4.5 Duration of Study

The total study duration for each vaccinated subject (assuming a screening period of 28 days) is 364 days.

4.6 Subject Selection and Sample Size

A total of approximately 60 participants will be enrolled in Phase 1a and approximately 54 participants in Phase 1b. Participants in Phase 1a will be randomized at 2:1 to VBI-2902a or placebo. Participants in Phase 1b will be randomized at 1:1 to receive one dose of VBI-2905a or placebo.

The Phase 1a and Phase 1b parts of the study are being conducted at clinical sites in Canada. For the Phase 1b part of the study, the sites will only enroll participants who have previously received mRNA COVID-19 vaccines.

With ~10% drop-out rate it is estimated that at least 56 participants will complete Phase 1a and 48 participants will complete Phase 1b. The sample size per active group will allow for the detection of at least a two-fold difference in nAb titers with 80% power and an alpha error of 0.05.

4.7 Study Vaccine Doses and Mode of Administration

During the screening visit participants will provide informed consent. Participants will remain at the study center for 60 minutes after vaccination and will be evaluated by study center personnel for AEs before discharge. The participants, site investigators and study site personnel performing outcome measurement and the sponsor will be blinded to vaccine allocation. Study vaccine will be administered by qualified unblinded study center staff.

4.8 Treatment Allocation

Phase 1a

In Phase 1a, VBI-2902a at a dose of 5 µg will be administered to participants 18-54 years of age. An Independent Data Safety Monitoring Board (DSMB) will perform an early review of blinded post-vaccination safety data at Day 7 after the first vaccination (reactogenicity, AEs and safety labs). The second vaccination will be given only if the DSMB confirms that early safety is acceptable and that stopping rules were not met.

The DSMB will further review blinded post-vaccination safety through Day 35, 7 days after the second vaccination and through Day 56, 28 days after the second vaccination. Enrollment in Phase 1b will commence once the DSMB confirms that safety data through Day 56 is acceptable and that stopping rules were not met.

The Study Steering Committee (SSC), comprised of representatives from the study sponsor (not involved in study operations) and external vaccine experts, will review unblinded immunogenicity data inclusive of Day 35, i.e., 35 days after the first (7 days after the second) vaccination, as well as Day 56, i.e., 56 days after the first (28 days after the second) vaccination from Phase 1a. Based on the pre-specified criteria for primary and secondary safety and immunogenicity endpoints, the Phase 1b dose and regimen of VBI-2905a may be modified.

Phase 1b

Phase 1b will evaluate the safety, tolerability and immunogenicity of a one-dose regimen of VBI-2905a at a dose level of 5 µg of S protein in healthy adults aged 18-54 years. DSMB will review blinded Day 7 safety data after the first 10 participants in each group have received their dose. Only after the DSMB

confirms that safety is acceptable and that stopping rules were not met will the enrollment in the respective study groups continue to its completion.

The SSC will review unblinded immunogenicity data 7 days and 28 days after the first vaccination,. Study participants will continue with study visits as planned up to 12 months of follow up after the first dose of study vaccine.

4.9 Blinding

This study is an observer-blinded study. Both participants and the study center staff performing outcome measurement are blinded; vaccines will be administered by qualified unblinded study personnel who have no other role in the study.

4.10 Endpoints

Primary Endpoints/Outcome Measures

- Rate and severity of local and systemic solicited adverse events (AEs) during 7 days after each study vaccination
- Rate and severity of unsolicited AEs during 28 days after each study vaccination
- Rate and severity of medically-attended adverse events (MAAEs) during 28 days after each study vaccination
- Rate of serious adverse events (SAEs) during 28 days after each study vaccination AEs leading to discontinuation of study vaccination
- AEs leading to study discontinuation
- Rate and severity of laboratory abnormalities (hematology, biochemistry, urinalysis) at Day 56 and 28 days after each study vaccination

Secondary Endpoints/Outcome Measures

- Rate and severity of unsolicited AEs throughout the study
- Rate and severity of medically-attended adverse events (MAAEs) throughout the study
- Rate of serious adverse events (SAEs) throughout the study
- Rate and severity of laboratory abnormalities (hematology, biochemistry, urinalysis) throughout the study
- GMT and the geometric mean fold increase in serum antibody titer post-vaccination over Day 1 (baseline) at Days 56 and 224 (Phase 1a) or Days 56 and 168 (Phase 1b):
 - Neutralizing activity against multiple variant spike protein-expressing pseudovirus, and/or PRNT neutralizing activity against wild-type SARS-CoV-2 virus and the variant Beta (B.1.351) in all participants
 - RBD antibody titers against wild-type variant spike protein measured by ELISA

- GMT and the geometric mean fold increase in serum antibody titer post-vaccination over Day 1 (baseline) at Days 7, 28, 35, 56, 112, 224 and 336 (Phase 1a); Days 7, 14, 28, 56, 84, 168 and 336 (Phase 1b)
 - Neutralizing activity against multiple variant spike protein-expressing pseudoviruses, and/or PRNT neutralizing activity against multiple variants of SARS-CoV-2 virus and the variant (B.1.351) in all participants
 - RBD antibody titers against wild-type variant spike protein measured by ELISA

Exploratory Immunogenicity Endpoints/Outcome Measures

- Geometric mean number of IFN- γ -positive cells per 10⁶ PBMCs by ELISPOT assay post-vaccination over Day 1 (baseline) at Days 7, 28, 35, 56 and 336 (Phase 1a); Days 7, 14, 28 and 336 (Phase 1b)

4.11 Data Collection

This study will be conducted in compliance with ICH CGP guidelines. This study will use electronic data collection (to collect data directly from the investigational site using eCRFs). The Investigator is responsible for ensuring that all sections of each eCRF are completed promptly and correctly. Data reported in the eCRF derived from source documents should be consistent with the source documents or the discrepancies should be explained. Study monitors will perform source document verification to identify inconsistencies between the eCRFs and source documents. Discrepancies will be resolved in accordance with the principles of GCP.

4.12 Safety Monitoring

Safety and tolerability will be evaluated throughout the study by collecting solicited local (injection site) and systemic AEs (reactogenicity) for 7 days post-vaccination, unsolicited AEs for 28 days postvaccination and medically-attended AEs (MAAEs) and serious AEs (SAEs) throughout the study. Participants will also be monitored by physical examinations, vital signs, and safety laboratory testing (hematology, serum chemistry, urinalysis). See [Table 1](#), and [Table 2](#) Schedules of Events, for details.

The safety population includes all participants who received at least one dose of the study vaccine. The baseline values for all laboratory evaluations and vital signs will be defined as the last evaluation done before the administration of the study vaccine on Day 1. Safety will be evaluated by examining the incidence and type of AEs, and changes in clinical laboratory test values, physical examination results and vital sign measurements from the screening phase through study completion across study groups.

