Safety and Immunogenicity Assessments	
Safety Assessments
 
Safety and tolerability will be evaluated throughout the study by collecting solicited local (injection site) and systemic AEs (reactogenicity) for 7 days post-vaccination, unsolicited AEs for 28 days postvaccination and medically attended AEs (MAAEs) and serious AEs (SAEs) throughout the study. Participants will also be monitored by physical examinations, vital signs, and safety laboratory testing (hematology, serum chemistry, urinalysis). See Table 1, and Table 2 , Schedules of Events, for details.
 
The safety population includes all participants who received at least one dose of the study vaccine. The baseline values for all laboratory evaluations and vital signs will be defined as the last evaluation done before the administration of the study vaccine on Day 1. Safety will be evaluated by examining the incidence and severity of AEs, and changes in clinical laboratory test values, physical examination results and vital sign measurements from the screening phase through study completion across study groups.
 
Immunogenicity Assessments
 
Immunogenicity will be assessed by measuring serum nAb titers against wild-type SARS-CoV-2 virus (PRNT) and/or spike protein-expressing pseudovirus (microneutralization), serum binding antibody titers against spike protein and the spike protein receptor-binding domain (RBD), and peripheral blood mononuclear cell (PBMC) T cell responses against spike protein. Testing will include assessment of responses against spike protein of the original SARS-CoV-2 isolate as well as spike protein of B.1.315 and other variants. In Phase 1a, time points for evaluation will be at Study Days 1, 7, 28, 35, 56, 112, 224 and 336. In Phase 1b, time points for evaluation will be at Study Days 1, 7, 14, 28, 56, 84, 168 and 336. Neutralizing antibody and binding antibody results will be presented as the geometric mean titer (GMT) and the geometric mean fold increase in titer post-vaccination over baseline. T cell responses will be presented as the geometric mean

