6.1.15 Recording of AEs, SAEs, and Potential Immune-Mediated Diseases

The participants will be instructed to contact the investigator/study personnel immediately should they manifest any signs or symptoms they perceive as serious (see [Section 8](#)).

At the vaccination visit, 7-day diary cards will be provided to the participant. The participant will record body temperature (oral) and any local/systemic adverse events (AEs)

(i.e., on the day of injection and during the next 6 days). The study center will contact the participant at 3 days (+/- 1 day) post-vaccination to assess participant status and to remind the participant to complete the diary cards. The participant will be instructed to return the completed diary card to the investigator/study personnel at the next study visit.

Any unreturned diary cards will be sought from the participant through telephone call(s) or any other convenient procedure. The investigator/study personnel will transcribe the collected information into the eCRF in English.

Diary cards are considered source documents.

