If any of the solicited local or systemic reactions persist beyond Day 7, these will also be recorded as an AE. In this case, the AE start will be set as 7 days post vaccination. The participant will be requested to note when the AEs resolves and report this information to the investigator or clinic staff at the next visit at the study center or contact.

The clinical importance of AE will be determined based upon the investigator's judgment. The investigator must ensure that any sample obtained to follow-up an AE is properly labeled and stored. The investigator and others responsible for care of the participants should institute any supplementary investigations of significant AEs based on the clinical assessment of the likely causative factor. This may include seeking the opinion of a specialist in the field of the AE.

All AEs occurring within 28 days after vaccination must be recorded in the study source documents at the site or Diary Cards and reported in the "Adverse Event" screen in the participant's eCRF, irrespective of intensity or whether or not they are considered vaccination-related. Thereafter, from Day 28 through completion of the Day 336 visit, participants will need to record all AEs in their Diary Cards. Adverse events, pregnancy and SAEs will be monitored and recorded in the eCRF. Serious adverse events and pregnancy will be reported to Pharmacovigilance.

Treatment Emergent Adverse Event (TEAE)

TEAE is an event that emerges during treatment having been absent pre-treatment, or worsens relative to the pre-treatment state (ICH E9). The period of observation for collection of TEAEs extends from the time the participant receives the first dose of study drug through the last study visit.

Medically-Attended Adverse Events (MAAE)

- A condition prompting emergency room visit, physician visit not related to a common disease/not a routine visit or an SAE not related to a common disease SAE.

Serious Adverse Event (SAE)

During clinical investigations, adverse events may occur which, if suspected to be medicinal product related (adverse drug reactions), might be significant enough to lead to important changes in the way the medicinal product is developed (e.g., change in dose, population, needed monitoring, consent forms).

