10.1.2 Secondary Endpoints/Outcome Measures

Rate and severity of unsolicited AEs throughout the study

Rate and severity of medically-attended adverse events (MAAEs) throughout the study Rate of serious adverse events (SAEs) throughout the study

Rate and severity of laboratory abnormalities (hematology, biochemistry, urinalysis) throughout the study

- GMT and the geometric mean fold increase in serum antibody titer post-vaccination over Day 1 (baseline) at Days 56 and 224 (Phase 1a) or Days 56 and 168 (Phase 1b):
 - Neutralizing activity against multiple variant spike protein-expressing pseudovirus, and/or PRNT neutralizing activity against wild-type SARS-CoV-2 virus and the variant Beta (B.1.351) in all participants
 - RBD antibody titers against wild-type variant spike protein measured by ELISA
- GMT and the geometric mean fold increase in serum antibody titer post-vaccination over Day 1 (baseline) at Days 7, 28, 35, 56, 112, 224 and 336 (Phase 1a); Days 7, 14, 28, 56, 84, 168 and 336 (Phase 1b)
 - Neutralizing activity against multiple variant spike protein-expressing pseudoviruses, and/or PRNT neutralizing activity against multiple variants of SARS-CoV-2 virus and the variant (B.1.351) in all participants
 - RBD antibody titers against wild-type variant spike protein measured by ELISA

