6.3 Safety Analyses

6.3.1 Adverse Events (AEs)

6.3.1.1 General Guidance on AEs

All AE related Tables and Listings will be analyzed using the SC. All adverse-events in the SC will be presented in listings. Only Treatment-Emergent Adverse Events (TEAEs) will be summarized in tables. TEAEs include: 1) AEs with an onset on or after the first vaccination dose and 2) AEs that worsen relative to the pre-treatment state. The period of observation for collection of TEAEs extends from the time the participant receives the first dose of vaccine through the last study visit.

Adverse events will be coded to the System Organ Class (SOC) and preferred term (PT) level using the Medical Dictionary for Regulatory Affairs (MedDRA dictionary).

TEAEs missing severity will be summarized as “missing” in summary tables.

The summary tables for unsolicited AEs will use the following algorithms for counting the subject:

- System Organ Class row: Subjects experiencing the same AE System Organ Class several times will only be counted once.
- Preferred term row: Subjects experiencing the same AE preferred term several times with different grades will only be counted once with the maximum grade.
- Any event row: Each subject with at least one adverse event will be counted only once at the maximum grade no matter how many events they have.

Unless otherwise stated, AEs will be ordered alphabetically by SOC and in descending order of frequency by PT.

The summary tables for the rate and severity of solicited AEs will be presented by the terms defined on the eCRF.

Other types of events collected are defined as follows:

- 1) Medically-Attended Adverse Events (MAAE) – A condition prompting emergency room visit, physician visit not related to a common disease/not a routine visit or an SAE not related to a common disease SAE.
- 2) Serious Adverse Event (SAE) – Any untoward medical occurrence that *at any dose* results in death, is life-threatening, requires hospitalization or prolongation of existing hospitalization, results in disability/incapacity, is a congenital abnormality/birth defect in an offspring of a study participant, or is another medically important event.

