6.3.1.2 AE Summaries

An overview summary of TEAEs including:

- 1) Counts and percentages of subjects
 - a. With any TEAE,
 - b. With any local solicited AEs during 7 days of vaccination dosing,
 - c. With any systemic solicited AEs during 7 days of vaccination dosing,
 - d. With any unsolicited AEs within 28 days of each vaccination dose,
 - e. With any unsolicited MAAEs at Day 56 and 28 days after each vaccination dose,
 - f. With any unsolicited SAEs at Day 56 and 28 days after vaccination dose,
 - g. With any unsolicited AEs leading to discontinuation of study vaccination,
 - h. With any unsolicited AEs leading to study discontinuation,
 - i. With any unsolicited AEs during the study,

j. With any unsolicited SAEs during the study.
will be presented stratified by treatment and age group.

For each type of AE noted in the overall summary point 2 except solicited AEs (2b and 2c), we will additionally produce summaries of the AEs by SOC and PT. Furthermore, summaries of event types 2d, and 2i will be presented for by SOC, PT, and severity (mild/moderate/severe/potentially life threatening).

Solicited AEs will be summarized separately for local AEs, systemic AEs, and fever >38 centigrade as collected on the solicited AEs eCRF pages. These summaries will be presented for each dose separately and cumulatively, will count the number of subjects experiencing at least one solicited AE, and will count the number of subjects experiencing at least one of each of the solicited AEs ordered per the solicited AEs eCRF pages.

Lastly, within the solicited AE by SOC/PT summary, 2-sided, alpha=0.05 Fisher's Exact tests will be performed to assess differences in rates of these adverse events between the treatment groups. No adjustment will be made to account for multiplicity of tests performed.

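### Protocol 4.12 and the synopsis stop unsolicited AE collection 28 days after vaccination, while a secondary endpoint and Protocol section 8 run it to Day 336, and the late capture tool is not specified

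*Protocol*

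**What the plan says.** **Collection period, short version.** Protocol 4.12 (Safety Monitoring) collects "unsolicited AEs for 28 days postvaccination" and, in the same sentence, MAAEs and SAEs for the whole study. The synopsis, under Safety and Immunogenicity Assessments, has the same sentence.

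**Endpoint, long version.** Protocol 4.10 and 10.1.2 and SAP section 2 list as a secondary endpoint "Rate and severity of unsolicited AEs throughout the study". The 28-day rate is listed separately as a primary endpoint. SAP 6.3.1.2 item i counts subjects "With any unsolicited AEs during the study", with further tables by SOC, PT and severity. SAP 6.3.1.1 adds: "The period of observation for collection of TEAEs extends from the time the participant receives the first dose of vaccine through the last study visit".

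**Late capture.** Protocol 8.1 says that "from Day 28 through completion of the Day 336 visit, participants will need to record all AEs in their Diary Cards", with AEs recorded in the eCRF.

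**The diary.** Protocol 6.1.15 says: "At the vaccination visit, 7-day diary cards will be provided to the participant". The card covers the injection day and the following six days and is returned at the next visit. Footnote 6 to the schedules of events ties it to vaccination visits and solicited reactions.

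**The concern.** The sentence in 4.12 sets unsolicited AEs against two event types that are followed to the end, so its 28 days reads as a limit. The whole-study endpoint is plainly deliberate, because the 28-day rate is a separate, primary endpoint. Both cannot be followed as written.

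A site that takes 4.12 as its rule would stop recording non-serious, non-medically-attended AEs after the 28-day window. A site that works from section 8 would continue to Day 336. The whole-study rate would then mix complete and incomplete ascertainment.

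The tables would not show the problem. SAP 5.1 takes percentages over all subjects in the treatment group unless stated otherwise, and SAP 5.4 imputes no missing data unless specified. A participant whose only event was late and uncollected is therefore counted as having had none, and the rate is biased downward. SAP section 7 declares no change from the protocol's planned analyses, so the SAP does not settle which period applies.

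**Working it through.** **Follow-up length.** Protocol 4.5 gives 364 days per participant including 28 of screening, and 6.1.16 ends the study at Day 336. Check: 28 + 336 = 364, which agrees. The whole-study endpoint is therefore taken over 336 days.

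**Days outside the 28-day windows if 4.12 is applied literally.** Formula: 336 minus the last day of the final window, using the protocol's own day labels and assuming dosing on the nominal day.

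- Phase 1a: doses on Days 1 and 28; last window ends at 28 + 28 = Day 56. 336 − 56 = 280 days; 280/336 = 83.3%.
- Phase 1b: one dose on Day 1; window ends at the Day 28 visit. 336 − 28 = 308 days; 308/336 = 91.7%. Counting literally to 1 + 28 = Day 29 gives 307 days, 91.4%.

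**Days covered by the 7-day card.** Formula: 7 × number of vaccinations.

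- Phase 1a: 7 × 2 = 14 days; 14/336 = 4.2%. Inside the 28-day windows, 56 − 14 = 42 days fall after the card ends.
- Phase 1b: 7 × 1 = 7 days; 7/336 = 2.1%. Inside the window, 28 − 7 = 21 days fall after the card ends.

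**Visit spacing after Day 56 (Protocol 4.1).** Phase 1a visits are on Days 112, 224 and 336, so the longest gap is 224 − 112 = 336 − 224 = 112 days. Phase 1b visits are on Days 84, 168 and 336, so the longest gap is 336 − 168 = 168 days. Without a working diary, minor events over such gaps depend on recall.

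**Provisions for new AEs, side by side.**

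| Place | Period |
|---|---|
| Protocol 4.12, first paragraph; synopsis | 28 days after vaccination |
| Protocol 4.12, second paragraph | AEs evaluated from screening to study completion |
| Protocol 8.1 | To Day 336, via Diary Cards and eCRF |
| Protocol 8.4 | All AEs from consent go into the eCRF; post-study events are those after Day 336 |
| Protocol 8.5 | Open question about changes since the last visit |
| Protocol 10.7.1 | Participants report any AE at any time in the study |
| TEAE definition (Protocol 8.1, SAP 6.3.1.1) | First dose to last visit |

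Protocol 8.8 also runs to Day 336, but it concerns follow-up of AEs already documented and so does not settle when new ones stop being collected.

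**The case against.** The best reply is that 4.12 is a summary paragraph. It refers to the schedules for detail, and its own second paragraph evaluates AEs to study completion. The operative rules are in section 8, and they point to Day 336: 8.4 places the end of the AE reporting period there, 8.5 supplies the question to ask at visits, and 10.7.1 tells participants to report events at any time. This stands. A reader might infer that the secondary endpoint cannot be supplied at all. The documents do not support that, because a site must follow section 8 as well as 4.12.

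A reader might also infer that the 7-day card is the only diary in the study. That is not supported either. Protocol 4.2 provides diary cards for recording any symptoms under COVID-19 surveillance, 8.1 allows diary recording of all AEs within 28 days, and 8.5 mentions entry in a participant diary. What remains is narrower: no issue, duration or return procedure is given for any diary beyond the 7-day card, although 8.1 depends on one for months.

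The size is also open to objection. The 83% and 92% are shares of calendar time, not of events, and they assume that the section 8 instructions are disregarded. MAAEs and SAEs are collected throughout even under 4.12. Late unsolicited AEs are summarised descriptively; Fisher's exact tests apply only to solicited AEs. Unblinding after Day 56 is planned and is not caused by this wording, though most of the disputed period is then unblinded.

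None of this removes the contradiction between 4.12 and the endpoint.

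**Conclusion.** The point holds as an internal contradiction, wrong as written and of minor severity. Two collection periods are stated for a named secondary endpoint, and the tool assigned to the longer one is not described.

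If 4.12 is applied, the loss is confined to late AEs that are neither serious nor medically attended. The worst case is 280 of 336 days in Phase 1a and 308 of 336 in Phase 1b, with the reported rate biased downward. That bound assumes nominal dosing days and sites that apply 4.12 over section 8. The true loss could be anything from none to that bound, and the documents give no event rates with which to convert days into events.

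The primary endpoint on unsolicited AEs uses the 28-day window, agrees with 4.12 and is unaffected. The AE row in the schedules of events is not used as evidence here, because its cell positions cannot be read in the available text.

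**What to change.** Reconcile the passages in one of two ways.

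1. **Keep the whole-study endpoint (preferred).** Amend Protocol 4.12 and the synopsis to say that unsolicited AEs are collected to Day 336 by questioning at each scheduled visit and recorded in the eCRF, in line with 8.1, 8.4 and 8.5. In 8.1, name the capture tool used after Day 28, and align 6.1.15 and footnote 6 with it. Keep the diary use within 28 days: 8.1 allows Diary Cards for AEs in that window, and those data serve a primary endpoint, so removing diaries after Day 7 would do harm.
2. **Keep the 28-day limit.** Restrict the secondary endpoint and SAP 6.3.1.2 item i to the 28-day windows, with MAAEs and SAEs thereafter, and bring section 8 and the TEAE period into line.

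If late events have already been collected under mixed rules, the SAP should state the period applied.

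The cost is wording in the protocol and, for the second option, the SAP. The first option adds no visit, since the visits to Day 336 already exist.
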